## 4.2 PRIMARY EFFICACY ENDPOINT ANALYSIS

## 4.2.1 Definition of Primary Endpoint/Estimand

The primary efficacy endpoint is the percent change from baseline in study eye ECD value at Year 1.

## 4.2.2 Main Analytical Approach for Primary Endpoint

Available corneal ECD values and percent change from baseline in ECD values will be summarized descriptively at baseline and at Year 1, for study and fellow eyes respectively.

In addition, the percent change in corneal ECD from baseline at Year 1 will be analyzed using the paired t-test comparing study and fellow eyes. P-value and 95% interval from the paired t-test will be provided.

Paired t-test will be performed among the subset of patients who had an interpretable baseline and Year 1 specular microscopic image in both eyes.

Paired t-test comparing study eyes and fellow eyes within each of the following subgroups will also be provided:

• Baseline age (<65,  $\ge 65$  to <75, and  $\ge 75$  years)

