## 6. STATISTICAL CONSIDERATIONS AND ANALYSIS PLAN

#### 6.1 DETERMINATION OF SAMPLE SIZE

No formal sample size calculations were performed for this substudy. A planned enrollment of approximately 135 patients from the *main* Study GR42691 was selected in order to obtain data from at least 100 patients through Year 1 to account for patients with missing data (e.g., missed visits, lost to follow-up). ECD, CV, and HEX will be assessed in the corneal endothelium evaluable set (modified intent-to-treat [mITT] population), which includes all patients who were treated in the study eye and for whom specular microscopic images were interpretable in both the study and fellow eye both at baseline and at the substudy midpoint and/or Year 1 evaluations.

For additional details, refer to main Study GR42691.

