### 6.5.3.1 Subgroup Analyses

The percent change in corneal ECD from baseline at Year 1, the percent change in CV of corneal endothelial cell area from baseline at substudy midpoint and Year 1, and the percent change of HEX cells from baseline at substudy midpoint and Year 1 will be analyzed separately using the paired t-test within each of the following subgroups:

- Baseline age (<65, ≥65 to <75, and ≥75 years)

- Number of faricimab injections received during substudy ( $\leq 5$ , > 5 injections)

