## 2. STATISTICAL HYPOTHESES AND SAMPLE SIZE DETERMINATION

#### 2.1 STATISTICAL HYPOTHESES

No formal hypothesis testing is planned for this study.

The paired t-tests are planned for efficacy analyses for reference purposes and thus not considered formal. In general, the paired t-tests will compare the percent change from baseline between the study eye and fellow eye in each CEC parameter described in

Faricimab—F. Hoffmann-La Roche Ltd **Statistical Analysis Plan** GR42691 CEC Substudy

Section 4.2, Section 4.3 and Section 4.4, respectively in the specified groups. The test will be 2-sided, with the null hypothesis of no difference in percent change from baseline between the study eye and fellow eye in each patient. P-values and 95% confidence interval of the difference from the paired t-tests will be provided.

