## 2.2 SAMPLE SIZE DETERMINATION

No formal sample size calculations were performed for this substudy. A total of 117 patients were enrolled in this substudy from the main Study GR42691.

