## 4.8 CHANGES TO PROTOCOL-PLANNED ANALYSES

Per-protocol analysis was removed from the analysis plan as the study intends to reflect the impact of treatment in a real-world setting, where participants may or may not adhere to a clinical study protocol when taking/receiving medication.

Adverse Event analyses, which were not specified in the protocol, are currently planned in this SAP document, in order to provide a comprehensive safety summary during the substudy, in light of the fact that a patient's duration on the CEC substudy could extend beyond the duration of the main study.

Analyses by the main Phase III study treatment group in this substudy will not be conducted. This is due to the fact that the substudy consists of a single treatment group (faricimab), which differs from the Phase III study that includes a comparative group.

The subgroup analysis based on the number of faricimab injections received during the substudy has been removed. This decision is made because participants enrolled in the substudy at different timepoints during the main study and received faricimab prior to the substudy enrollment. Hence, the injection numbers received during the substudy do not accurately represent the cumulative exposure to faricimab in the patients, rendering such analysis less clinically meaningful and potentially misleading.

Subgroup analyses of primary and secondary endpoints by age are considered sufficient to understand the effect of age on efficacy, hence no further subgroup analyses are planned for exploratory endpoints.

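### Separate paired t-tests in three age bands do not assess whether the eye difference varies with age, yet SAP 4.8 calls them sufficient for understanding the effect of age

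*SAP*

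**What the plan says.** SAP 4.2.2 (Main Analytical Approach for Primary Endpoint), on ECD at Year 1: "Paired t-test comparing study eyes and fellow eyes within each of the following subgroups will also be provided". The only subgroup factor is baseline age, in three bands: under 65, 65 to under 75, and 75 and over. SAP 4.3 applies the methods of 4.2 to ECD at midpoint. SAP 4.4 does the same for CV and HEX, but without subgroups.

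SAP 2.1 defines what each test asks: "The test will be 2-sided, with the null hypothesis of no difference in percent change from baseline" between the two eyes. On output it says: "P-values and 95% confidence interval of the difference from the paired t-tests will be provided". On status it says: "The paired t-tests are planned for efficacy analyses for reference purposes and thus not considered formal".

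SAP 4.8 (Changes to Protocol-planned Analyses) says: "Subgroup analyses of primary and secondary endpoints by age are considered sufficient to understand the effect of age on efficacy". It gives this as the reason for planning no subgroup analyses of the exploratory endpoints.

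Protocol 6.5.3.1 already used separate paired t-tests within the same age bands, and included CV and HEX. Neither document plans a contrast between bands, an interaction test or age as a covariate.

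**The concern.** The stated purpose and the method do not match. Whether the effect of treatment depends on age is a question about how the study-minus-fellow difference changes across ages. The plan instead asks three times whether that difference is zero, and a p-value in one band depends heavily on how many patients the band holds. If one band reaches significance and another does not, a reader may take this for an age effect when chance and band size are enough to produce it. Conversely, no planned analysis uses all patients to look for a trend.

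Age is not an arbitrary factor here. Protocol 1.2 and SAP 1 both say that cell density and the percentage of hexagonal cells fall with age. SAP 4.8 also removes, for separate reasons, the injection-count subgroup and the analyses by Phase III treatment group, so age is the only subgroup factor left.

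**Working it through.** **1. What the documents supply.** There is no power calculation to reproduce. Protocol 6.1 plans about 135 patients "in order to obtain data from at least 100 patients through Year 1 to account for patients with missing data". SAP 2.2 reports: "A total of 117 patients were enrolled in this substudy from the main Study GR42691". Applying the planned ratio gives 117 × 100/135 ≈ 87 evaluable patients; the planned minimum is 100 and the ceiling is 117. The documents give no age distribution, SD of the paired difference, effect size or significance level.

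**2. Assumptions.**
- N = 87, 100 or 117 evaluable patients.
- Band splits from about 5/35/60% to equal thirds.
- The same standardized effect d = mean/SD of the paired difference in every band.
- Two-sided 0.05, inferred from the 95% intervals.

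**3. Formula.** The bands contain different patients, so their tests are independent. Let pᵢ be the noncentral-t power of the paired t-test in band i, with nᵢ − 1 degrees of freedom and noncentrality d√nᵢ. Then

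P(mixed) = 1 − p₁p₂p₃ − (1 − p₁)(1 − p₂)(1 − p₃),

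where mixed means that at least one band, but not all three, has p < 0.05.

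**4. One case in full.** N = 100 split 10/30/60, with 80% overall power (d = 0.283). The band powers are 0.126, 0.322 and 0.578.
- All significant: 0.126 × 0.322 × 0.578 = 0.024.
- None significant: 0.874 × 0.678 × 0.422 = 0.250.
- Mixed: 1 − 0.024 − 0.250 = 0.726.

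**5. The range.**

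| Overall power (N = 100) | d | Band powers, 10/30/60 | P(mixed), 10/30/60 | P(mixed), all N and splits |
|---|---|---|---|---|
| zero effect | 0 | 5%, 5%, 5% | 14% | 14% |
| 20% | 0.113 | 6%, 9%, 14% | 26% | about 26% |
| 50% | 0.198 | 9%, 18%, 33% | 49% | 48–50% |
| 80% | 0.283 | 13%, 32%, 58% | 73% | 68–74% |
| 90% | 0.327 | 15%, 41%, 70% | 81% | 74–83% |

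At zero effect the figure is 1 − 0.05³ − 0.95³ = 0.143. For a very large effect it falls again: 39% at d = 0.8 with the 10/30/60 split.

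**6. A direct comparison of bands.** A one-way ANOVA of the within-patient difference across the same 10/30/60 bands was simulated 10,000 times at each of d = 0, 0.285 and 0.4, with the effect identical in all bands. It rejected in 4.7%, 5.0% and 5.2% of trials. In the same trials the separate t-tests were mixed in 14%, 73% and 85%.

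**7. Precision.** The half-width of the 95% CI within a band, in SD units, is t(0.975, n − 1)/√n: 0.72 for n = 10, 0.37 for n = 30 and 0.26 for n = 60, against 0.20 for all 100. For a contrast between two bands it is t(0.975, 97) × √(1/nₐ + 1/n_b), with t = 1.985: 0.72 (10 v 30), 0.68 (10 v 60) and 0.44 (30 v 60). A linear slope uses all 100 patients. In a simulation with a linear trend its test had 83% power for a trend of 0.3 SD of the difference per SD of age, and 50% for 0.2.

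**The case against.** The strongest reply is that nothing formal depends on these tests. SAP 2.1 plans no formal hypothesis testing, age is not a substudy objective, and the post-marketing requirement quoted in SAP 1 does not mention age. That stands, and it keeps the point minor. It does not make the tests sufficient for the purpose that SAP 4.8 gives them.

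The intervals also count. Because the bands are independent, a reader can derive an approximate contrast from the per-band 95% CIs, so it would be too strong to say that the output carries no information about age. But the SAP neither plans nor reports such a contrast.

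Three stronger readings are tempting, and the documents do not support them:
- *Mixed significance is likely whatever the effect.* It is likely only for a moderate common effect. Protocol 3.3.3 takes current evidence to show no negative effect of anti-VEGF agents on the corneal endothelium. Under that premise the figure is near 14%, although Protocol 1.3 says that faricimab itself has not been studied.
- *SAP 4.8 uses the age argument to drop all other subgroup work.* It uses it only for the exploratory endpoints. The injection-count subgroup was removed on a separate ground, namely that injections during the substudy do not represent cumulative exposure.
- *The under-65 band is known to be small, so any disagreement reflects only band size.* No age distribution is given, and chance or a real age difference could also produce disagreement. At 80% power the mixed result is 68–69% even with equal thirds.

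**Conclusion.** The point holds as a minor one. That the planned tests do not compare ages follows from the text and needs no assumption: no analysis in either document estimates how the eye difference changes with age, and *sufficient* in SAP 4.8 claims more than the method gives. How often the output would mislead does rest on assumptions. With an identical effect in every band, disagreement on significance runs from about 14% of trials at zero effect, through 26% and 50%, to 68–74% at 80% overall power. These figures are conditional on assumed band sizes, a common standardized effect and a 0.05 threshold that the SAP does not state. The primary comparison of study and fellow eyes is not affected.

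**What to change.** - For ECD at Year 1 and at midpoint, add one linear regression of the within-patient study-minus-fellow difference in percent change on continuous baseline age. Report the slope with its 95% CI as the exploratory assessment of age.
- Present the three bands as means with 95% CIs, and state that differences between band p-values will not be interpreted as an age effect.
- Reword SAP 4.8 so that it no longer calls the band analyses sufficient for the effect of age, and give the reason for omitting CV and HEX subgroups in terms that do not depend on that claim.

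The cost is one model per ECD endpoint. It needs no new data, since SAP 4.6.2 already derives baseline age from the date of the baseline image. There are two downsides. The regression assumes a roughly linear trend, which the band means allow one to check by eye. Precision at about 100 patients is limited, so a small age trend could still be missed, and a slope interval that includes zero should not be read as showing that age has no effect.

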#### 4.3 SECONDARY EFFICACY ENDPOINT ANALYSIS

The secondary efficacy endpoint is the percent change from baseline in study eye ECD value at midpoint. The secondary endpoint will be analyzed using the same analysis methods as the primary endpoint, as described in Section 4.2.

Faricimab—F. Hoffmann-La Roche Ltd

Statistical Analysis Plan GR42691 CEC Substudy

## 4.4 EXPLORATORY EFFICACY ENDPOINT ANALYSIS

Exploratory endpoints include:

- Percent change in the coefficient of variation of corneal endothelial cell area (standard deviation of the cell area/mean cell area) from baseline at substudy midpoint and Year 1 in the study eye
- 2. Percent change of hexagonal endothelial cells from baseline at substudy midpoint and Year 1 in the study eye

Exploratory endpoints will be analyzed using the same analysis methods as the primary endpoint, as described in Section 4.2, with the exception that subgroup analyses will not be performed for exploratory endpoints.

### 4.5 SAFETY ANALYSES

Safety analyses will be performed using the safety evaluable population, all data points collected will be used. Missing data will not be imputed.

## 4.5.1 Extent of Exposure

Exposure to faricimab treatment (number of treatments and duration of treatment) in the study eye during the substudy will be summarized using the safety evaluable set. Faricimab treatment in the study eye after completion of AVONELLE-X will be included.

The exposure period will be calculated from the screening/Day 1 CEC image taken date to the last faricimab injection (including injections during AVONELLE-X or after the AVONELLE-X completion as concomitant medication) in the study eye or last dose hold, whichever is later.

## 4.5.2 Adverse Events

All Adverse Events (AEs) during the substudy are reported in the main study GR42691 database. If a patient's duration on the CEC substudy extends beyond the duration of the main study, safety data will continue to be collected per the same reporting mechanism as the main study period until the final CEC substudy visit. Only AEs occurring during the substudy will be analyzed, which is defined as any new adverse event reported or any worsening of an existing condition on or after the substudy screening in this CEC substudy.

All verbatim AEs terms will be coded using the latest version of Medical Dictionary for Regulatory Activities (MedDRA).

Non-ocular AEs will be tabulated by System Organ Class (SOC) and Preferred Term (PT). Ocular AEs in the study eye will be tabulated by PT.

Frequency tables, including patient incidence rates, will be provided for the adverse events listed below. Ocular AEs will be reported for study eyes. Selected summaries and listings of AE in the fellow eyes may be provided.

- Ocular AEs and serious adverse events (SAEs)
- Ocular AEs by severity
- Adverse events of special interest (AESI) defined as follows:
  - Cases of potential drug-induced liver injury that include elevated alanine aminotransferase or aspartate aminotransferase in combination with either an elevated bilirubin or clinical jaundice, as defined by Hy's Law (see Section 5.2.3 of the main study protocol)
  - Suspected transmission of an infectious agent by the study drug
  - Sight-threatening AEs (see Section 5.2.3 of the main study protocol for the definitions)
- Selected ocular AEs
  - Intraocular inflammation
  - Infectious endophthalmitis
  - Retinal vascular occlusion
- Treatment related ocular AEs and SAEs as determined by the investigator
- AEs leading to discontinuation from AVONELLE-X
- AEs leading to discontinuation of AVONELLE-X study treatment
- AEs leading to interruption of AVONELLE-X study treatment
- Non-ocular AEs and SAEs
- Non-ocular adverse events of arterial thromboembolic event (ATE) and cerebrovascular haemorrhagic adverse events
- Externally adjudicated APTC events
- Deaths

As there is no standardized MedDRA queries (SMQ) encompassing the medical concepts of intraocular inflammation (IOI), infectious endophthalmitis or retinal vascular occlusion, the definitions will be assessed based on the review of clinical database PTs or reported AEs from clinical database prior to data cut and final database lock, and with subsequent MedDRA version updates, to ensure no event terms are missed.

Listings of AEs, SAEs, AESIs, APTCs, ATEs, Intraocular Inflammation and deaths will be provided.

A listing of AEs, including ocular AEs in the study eye and non-ocular AEs, occurring to the patient at GCP noncompliance affected site (described in Section 3) will be provided.

## 4.5.3 Additional Safety Assessments

No additional safety assessments, laboratory data, vital signs or ocular assessment, were planned for this substudy. No summaries are planned.

#### 4.6 OTHER ANALYSES

## 4.6.1 Summaries of Conduct of Study

Patient disposition including the number of participants enrolled and completing the entire substudy will be summarized in the mITT set. Reasons for premature substudy discontinuation will be tabulated. Listing of substudy discontinuations will be provided. Detailed, free text reasons for discontinuations due to physician decision, withdrawal by subject and 'other' reasons will be included in the listing.

The number of participants will be tabulated by country and site.

Eligibility criteria and other major protocol deviations will be tabulated in the mITT set, and a listing will be provided.

## 4.6.2 Summaries of Treatment Group Comparability

There is only one treatment group in the main study therefore, comparability across treatment groups is not applicable. Clinically important demographics will be summarized using the mITT set. The variables will be summarized using means, standard deviations, medians, and ranges for continuous variables, as well as using counts and proportions for categorical variables. The baseline summary will include:

- Age
- Sex
- Race
- Ethnicity
- Disease characteristics (BCVA, CST, etc)

Demographic data (e.g., sex and race or ethnicity) will originate from the main Phase III studies. Baseline age will be calculated using the date of baseline CEC image.

Baseline ocular disease characteristics (e.g., baseline BCVA, CST) will be assessed with values originating from the main study (GR42691).

Baseline ocular characteristics collected at the substudy screening visit will be summarized by eye (study eye versus control eye).

## 4.6.3 Pharmacokinetic Analyses

Not planned for this substudy.

## 4.6.4 Immunogenicity Analyses

Not planned for this substudy.

## 4.7 INTERIM ANALYSES

No interim analysis is planned for this substudy.

## 4.8 CHANGES TO PROTOCOL-PLANNED ANALYSES

Per-protocol analysis was removed from the analysis plan as the study intends to reflect the impact of treatment in a real-world setting, where participants may or may not adhere to a clinical study protocol when taking/receiving medication.

Adverse Event analyses, which were not specified in the protocol, are currently planned in this SAP document, in order to provide a comprehensive safety summary during the substudy, in light of the fact that a patient's duration on the CEC substudy could extend beyond the duration of the main study.

Analyses by the main Phase III study treatment group in this substudy will not be conducted. This is due to the fact that the substudy consists of a single treatment group (faricimab), which differs from the Phase III study that includes a comparative group.

The subgroup analysis based on the number of faricimab injections received during the substudy has been removed. This decision is made because participants enrolled in the substudy at different timepoints during the main study and received faricimab prior to the substudy enrollment. Hence, the injection numbers received during the substudy do not accurately represent the cumulative exposure to faricimab in the patients, rendering such analysis less clinically meaningful and potentially misleading.

Subgroup analyses of primary and secondary endpoints by age are considered sufficient to understand the effect of age on efficacy, hence no further subgroup analyses are planned for exploratory endpoints.

